### **c) Potential Risks**

Given the content of the questions and data collection methodologies, we anticipate minimal risk to participants. Answering questions about personal feelings and participating in the social stressor situation as part of the Trier Social Stress Task may have risk of causing emotional distress, particularly for participants who are experiencing high levels of social anxiety. The TSST-C has been well-validated for use in youth populations (Buske-Kirschbaum et al., 1997; Stroud et al., 2009) and has been widely used without causing undue risk to participants. For participants who are randomized to the conditions that involve interacting with a dog, there is always minor risk associated with interacting with live animals.

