## **2. Adequacy of Protection Against Risks**

### **a) Recruitment and Informed Consent**

Participants will be recruited from the Massachusetts area by leveraging advertisement through Tufts University resources (e.g., Tufts University School of Medicine, existing contacts through the Tufts Paws for People group, local clinics and educational programs). Flyers and email announcements will be sent to relevant listserves.

Consent for completing the brief online screening tool will be obtained digitally. Upon clicking on screening survey link, parent will be asked to complete a permission form for their child's participation. After parental consent/permission is received, the survey will direct to an assent form that youth will be asked to read and respond to. If youth agree to participate in the screening survey, they will then be directed to the survey.

For participants who are eligible to participate in the experiment, parental consent and youth assent will be obtained in person. A CITI-certified researcher will explain the nature of the study, and the risks, and parents/guardians will be asked to respond to a hard copy consent form. If the parent consents, then the youth participant will be asked to read and respond to a similar assent form. All participants and their parent/guardian will be reminded that they can choose to not participate in the study without any consequences, and that they may discontinue at any time once the study has begun.

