### **b) Protection Against Risks**

As noted above, there are minimal risks associated with this study. Although risks are minimal, we will provide participants with the PI's contact information should any questions or concerns arise, as well as provide contact information for mental health resources. We will also highlight the participant's right to discontinue his or her participation in any part of the study (including the TSST-C) at any time. If a participant becomes distressed during the TSST-C, the study will be stopped immediately, and the participant and his or her parent/guardian will be provided with contact information for a mental health professional.

As noted above, confidentiality of digital data will be maintained by assigning a four digit ID number to each participant that will be stored securely in REDCap. De-identified data files and video data files will be stored on a secure Tufts University server and will only be accessible by the PI and the co-investigators.

The animals participating in this study will be therapy dogs who are registered through Pet Partners® and members of Tufts Paws for People, reducing the risk of adverse events. The animals will always be accompanied by their handlers, who are required by Pet Partners to have their dogs on leash at all times while visiting and have been trained to advocate for their animals to ensure safety of all participants. As part of their Pet Partners training, all animal handlers have completed an 8-hr training course and their animals have passed a rigorous evaluation (with re-evaluation every 2 years) to meet training, safety, and health standards that protect both the animal-handler team and the people and facilities they are visiting. The animals are bathed 24 hours prior to participating in any program, and the teams are covered by comprehensive liability insurance through Pet Partners.

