### **5. Data Safety and Monitoring Plan**

**Safety Monitoring:** Given the content of the questions and data collection methodologies, we anticipate minimal risk to participants. Answering questions about personal feelings and participating in the social stressor situation as part of the Trier Social Stress Task may have risk of causing emotional distress, particularly for participants who are experiencing high levels of social anxiety. The TSST-C has been well-validated for use in youth populations and has been widely used without causing undue risk to participants. For participants who are randomized to the conditions that involve interacting with a dog, there is always minor risk associated with interacting with live animals.

Although risks are minimal, we will provide participants with the PI's contact information should any questions or concerns arise, as well as provide contact information for mental health resources. We will also highlight the participant's right to discontinue his or her participation in any part of the study (including the TSST-C) at any time. If a participant becomes distressed during the TSST-C, the study will be stopped immediately, and the participant and his or her parent/guardian will be provided with contact information for a mental health professional. If any minor skin irritation or discomfort takes place as a result of wearing the E4 wristband, it will be removed immediately.

The animals participating in this study will be therapy dogs who are registered through Pet Partners® and members of Tufts Paws for People, reducing the risk of adverse events. The animals will always be accompanied by their handlers, who are required by Pet Partners to have their dogs on leash at all times while visiting and have been trained to advocate for their animals to ensure safety of all participants. The animal handlers are trained to recognize stress signals in their dogs and will discontinue participation immediately if the therapy animal becomes stressed.

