### *Analyses:*

To test our confirmatory hypotheses, we conducted two three-way analyses of variance (ANOVA) with either self-reported anxiety (STAI), autonomic reactivity (electrodermal activity [EDA] and heart rate [HR]) as the dependent variable. For these outcomes, there were two between-subjects factors, condition (social, social + physical, control) and social anxiety (SA; centered continuous predictor), and one within-subjects factor, time point (1, 2, 3, 4, 5, 6). We included baseline STAI, EDA, or HR at time point 1 as a centered continuous covariate. For cognitive performance, we conducted ANOVAs that treated condition as a between-subjects categorical factor and social anxiety as a centered continuous predictor.

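### The six-level repeated-measures ANOVA names no sphericity correction and no rule for a missing phase; a suitably specified mixed model on phases 2 to 6 is the better primary analysis

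*SAP*

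**What the plan says.** The SAP's Analyses section states "we conducted two three-way analyses of variance (ANOVA") for STAI, electrodermal activity (EDA) and heart rate (HR). Condition and centred SAS-A score are the between-subject terms, with "one within-subjects factor, time point (1, 2, 3, 4, 5, 6"). It adds: "We included baseline STAI, EDA, or HR at time point 1 as a centered continuous covariate". Time point 1 is therefore both a level of the outcome and a covariate. Neither document gives a sphericity test or correction, a covariance structure, or a method for a participant with a missing phase.

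The protocol foresees partial sessions in three ways:

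- Distress (Protection Against Risks): "If a participant becomes distressed during the TSST-C, the study will be stopped immediately". Potential Risks says the questions and the stressor "may have risk of causing emotional distress, particularly for participants who are experiencing high levels of social anxiety".
- Choice (Recruitment and Informed Consent): participants are told "they may discontinue at any time once the study has begun".
- Device, for HR and EDA (Data Safety and Monitoring Plan): "If any minor skin irritation or discomfort takes place as a result of wearing the E4 wristband, it will be removed immediately".

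The protocol gives no expected rate for any of these, and it also says "we anticipate minimal risk to participants".

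**The concern.** **Sphericity.** An uncorrected within-subject F test assumes that all differences between pairs of phases have the same variance. Rest, anticipation, preparation, speech, arithmetic and recovery follow one another in a single session, so adjacent phases plausibly correlate more than distant ones. If so, the tests involving time reject too often, even with complete data. These tests belong to the models that the SAP calls confirmatory.

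**Missing phases.** A conventional repeated-measures ANOVA uses only participants with every phase. A session stopped during the speech would lose the phases already recorded as well as the later ones. Stops for distress plausibly depend on the outcome and on SAS-A, the Aim 2 moderator, so the remaining sessions may be a selected set.

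**Time point 1 as a level.** Once the time-1 value is the covariate (with its slope free to differ by phase, as in standard repeated-measures procedures), the adjusted difference between conditions at time 1 is zero by construction. That level carries no information about treatment.

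**Working it through.** **1. Inputs.** From the SAP's Sample Size Calculation: 25 per group, STAI SD 10.5 and difference 10, HR SD 12 and difference 12, alpha 0.05. The stated sizing reproduces with a two-sided two-sample t test: HR power is 90.0% at 22 per group (just short of the target) and 91.3% at 23; STAI power is 91.0% at 25. The sizing is not in dispute and only supplies inputs here. Correlations, stopping rates and stressor-phase means are assumptions, because the documents give none.

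**2. Sphericity, complete data.** Three arms of 25, six levels, baseline and SAS-A in the model, no true effects, 6,000 replicates (Monte Carlo SE at 5%: √(0.05 × 0.95 / 6000) = 0.3 points). The departure is measured by ε = (tr M)² / [(k−1) tr(M²)], where M is the double-centred covariance and k = 6; ε = 1 means sphericity holds.

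| Assumed correlation | Average estimated ε | Condition × time | Same, Greenhouse-Geisser | Condition × SAS-A × time |
|---|---|---|---|---|
| AR(1) 0.5 | 0.75 | 6.5% | 4.9% | 6.6% |
| AR(1) 0.7 | 0.69 | 7.7% | 4.6% | 7.2% |
| AR(1) 0.8 | 0.63 | 8.2% | 5.3% | 8.3% |
| Compound symmetry | near 1 | 5.2% | – | 5.2% |

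Repeat runs gave 6.3 to 8.4% for the AR(1) rows. The time-averaged condition and condition-by-SAS-A tests stayed near 5% (5.7% and 5.0% in one run at AR(1) 0.8). A multivariate test on phases 2 to 6, equivalent to unstructured covariance on complete data, rejected 4.2 to 5.5%.

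**3. Dropping incomplete sessions.** Assumptions: compound symmetry 0.7, SAS-A–STAI correlation 0.5, a stop when the speech-phase STAI exceeds 60, later phases then missing, 4,000 replicates. The estimate is the baseline-adjusted mean of phases 2 to 6. Control speech means of 40, 45 and 50 give control stopping of 2.9%, 7.6% and, as an upper case, 17.1% (0.7, 1.9 and 4.3 of 25). Stopping in the dog arms is 0.2 to 2.8%.

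| Quantity | 3% | 8% | 17% |
|---|---|---|---|
| True STAI effect −10, complete sessions only | −9.86 | −9.61 | −9.30 |
| Understatement | 1.4% | 3.9% | 7.0% |
| Same, all observed phases | −10.02 | −9.98 | −10.00 |
| Power for a 5-point effect, complete sessions only (about 91% with full data) | 90% | 88% | 82% |
| Aim 2 slope, true −4 | −3.85 | −3.68 | −3.46 |
| Aim 2 slope, true 0 | 0.18 | 0.25 | 0.39 |
| Aim 2 slope, true +4 | 4.07 | 4.16 | 4.23 |

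The slope shift at 3 to 8% stopping is about 0.1 to 0.3, against a standard error of 1.35 to 1.48. Rejection at a true slope of 0 stays at 4.9 to 5.2%. With no dog effect, the bias in the condition contrast is −0.02 to 0.02 and rejection 4.8 to 5.6%. For HR (true −12 bpm, HR–STAI correlation 0.2 and 0.5), 8% stopping gives −11.92 and −11.81, that is 0.08/12 = 0.7% and 0.19/12 = 1.6% too small. Wristband removal was not simulated.

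**4. Which mixed model.** On one balanced data set, a random-intercept model returned the same condition-by-time F as the uncorrected ANOVA (0.9124 for both), because it too assumes compound symmetry. An AR(1) structure is unsafe in the other direction. When the true correlation is 0.7 between all phases, AR(1) fits to phases 2 to 6 rejected the phase-averaged condition contrast in 8.3 to 9.4% of null trials, and the averaged condition-by-SAS-A slope in 8.7%. The ANOVA holds about 5% there.

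**5. Limit of using observed phases.** If the score at the distressing phase is itself unrecorded, the all-observed estimate is −9.82 at 8% stopping (full data −9.98) and −9.66 at 17% (full data −10.00). About half the bias remains: 0.16 against 9.98 − 9.61 = 0.37, and 0.34 against 10.00 − 9.30 = 0.70. The all-observed results use a sequential-regression likelihood fit; Kenward-Roger itself was not run.

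**The case against.** The strongest reply is that the SAP is silent rather than wrong. It does not say that incomplete sessions are dropped or that the F tests are uncorrected, and one sentence naming Greenhouse-Geisser would cure the sphericity part. That stands: deletion is inferred from the method, and the correction is offered below as the minimum. It is also fair that Aims 1 and 2, as worded in the protocol's Approach section, name no time interaction, and that the deletion bias is minor and rests on assumed rates and an assumed STAI trigger. The protocol ties stopping to distress, not to a score.

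Several stronger readings are tempting, but the documents do not support them:

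- A reader might infer that all the confirmatory tests are inflated. Only those involving time are.
- A reader might infer that distress stops could create a false dog effect. With no effect there is no bias, and a true effect is understated.
- A reader might infer that any mixed model solves both problems. Step 4 shows otherwise, and step 5 shows the dependence on missing at random.
- A reader might note that STAI power falls to 89.8% at 24 per group and conclude that one lost session per arm breaks the design. That figure belongs to the unadjusted two-group test used for sizing. Under the step 3 assumptions, the baseline-adjusted analysis had 100% power for 10 points in 2,000 runs, before and after deletion.

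What survives is that the plan fixes a method with two known weaknesses, while the protocol describes the partial sessions that expose one of them.

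**Conclusion.** The point holds in this limited form and should be acted on. The sphericity part needs no missing data: rejection of about 6.5 to 8.5% instead of 5% for the two interactions with time, if correlation decays as AR(1) 0.5 to 0.8, and about 5% if it does not decay. The missing-phase part is smaller: about 1 to 4% understatement of a 10-point STAI effect at 3 to 8% control stopping (7% at 17%), a modest loss of precision, and a slope shift well inside its standard error. For the condition effect the bias is towards the null. For Aim 2 the shift is slightly upward, so a negative slope is understated and a positive one slightly overstated. Confidence is medium, because every correlation and stopping rate is assumed.

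**What to change.** **Preferred.** Analyse STAI, HR and EDA at phases 2 to 6 with a linear mixed model: condition, time, SAS-A and their interactions, with time point 1 as covariate only. Use REML, unstructured covariance and Kenward-Roger degrees of freedom. Include every observed phase from all randomised participants with a recorded baseline; a session without one is still lost.

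**Fallback.** Five phases give 5 × 6 / 2 = 15 covariance parameters with 75 participants, so the unstructured fit may fail. Do not then use AR(1). Name in advance a structure that allows a persistent person effect, such as heterogeneous Toeplitz or random intercept plus AR(1), or robust standard errors with a small-sample correction.

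**Minimum if the ANOVA is kept.** Apply Greenhouse-Geisser to every test involving time, remove time point 1 as a level, and state the rule for missing phases.

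**In either case.** Report incomplete sessions by condition, SAS-A level and reason (distress, choice, wristband removed). Add a sensitivity analysis that imputes the phases missed after a distress stop and shifts them unfavourably, for example by about half and one SD (5 and 10 STAI points; 6 and 12 bpm). The mixed model is valid only under missing at random.

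**Timing and cost.** The Analyses section is in the past tense. If the ANOVA has already been run, report the mixed model alongside it, labelled post hoc. The cost is SAP wording, a standard procedure and one sensitivity analysis, with no new data or participants. The stopping rule is left unchanged.

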Our primary goal is to test the mechanism by which AAIs reduce anxiety (**Aim 1**). There are at least two possible hypotheses for the processes underlying anxiety reduction in AAIs. First, social support is broadly associated with beneficial psychological and physiological functioning (for review, see Uchino, Cacioppo, & Kiecolt-Glaser, 1996). In particular, social support can buffer the effects of laboratory based stressors (Heinrichs et al., 2003). According to Social Baseline Theory (Coan & Sbarra, 2015), humans are inherently social, and evaluate challenges based on their ability to meet goals. Part of this implicit calculation includes social relationships (e.g. friends, family, colleagues) that might be helpful in meeting goals. One possibility is that when a person interacts with an animal, a relationship is formed that becomes part of the person's representation of social resources. For instance, being around a friendly dog might decrease the possibility of being surprised by another human or animal, thus reducing risk and decreasing anxiety. Therefore, the first mechanism we will test is whether social interaction with an animal buffers anxiety in the presence of a social stressor.

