The primary task all participants will complete is the Trier Social Stress Task for Children (TSST-C), which involves six distinct phases: baseline, anticipation, preparation, speech, mental math, and recovery (Buske-Kirschbaum et al., 1997). The TSST-C (as well as the adult version of the TSST) has been used extensively as a robust and reliable method for inducing social stress, and variants have been used in conjunction with animal interaction (e.g., Allen et al., 2002; Polheber & Matchock, 2013). The TSST-C was originally validated for use in 10-14 year olds (Buske-Kirschbaum et al., 1997), but the protocol used in this study is a specific adaptation validated for use in adolescents up to 17 years old (Stroud et al., 2009). The TSST-C involves a public speaking task and a mental arithmetic performance challenge. During the baseline rest period (20 minutes) rest period, participants will watch a science documentary (with no animal content) on a digital tablet. Participants will then be told about the task (anticipation). Then participants will have a 5-minute preparation period, and then they will be asked to speak on an academic topic for 5 minutes (e.g., give a plot summary and interpretation of a book of their choice). They will then be asked to complete a serial subtraction mental arithmetic task for 5 minutes. Per the Stroud et al. (2009) protocol, the serial subtraction task will be adjusted for age (13-14 year olds will subtract by 11s, 15-17 year olds will subtract by 17s). If an error is made, participants will be instructed to restart from the beginning.

Finally, there will be a 30-minute recovery period where they will continue to watch the science documentary. Throughout the TSST-C, participants will be asked to self-report their anxiety levels at each of the 6 phases and will wear a watch-like wristband (Empatica E4) to continuously measure heart rate data.

Compensation for the screening process will be a \$10 gift card (duration approximately 10 minutes). Youth who meet the eligibility criteria and who participate in the experiment will be compensated with a \$75 gift card (duration of the study approximately 2 hours, not including travel time to Tufts University).

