## Statistical Analysis Plan

### *Sample Size Calculation:*

To estimate the sample size, we used heart rate (HR) as the primary outcome and the STAI (state subscale) as the secondary outcome. There are no prior data with which to estimate the relative effect of the two intervention and control conditions on the proposed outcomes. Therefore, estimates were compiled from other research using HR as an indicator of stress response (e.g., Greenland et al., 1999). In this situation, the most conservative approach for sample size calculation is to assume a series of two-way tests. We used a mean of 75 beats per minute (bpm) with a  $SD$  of 12 bpm for baseline in all groups, assuming normal distribution, an equal number of subjects in each group, and a 0.05 significance level (alpha). With these assumptions, we will have 90% power to detect a difference of 12 bpm between any two treatment groups with 23 subjects per group, which we round to 25 per group for a total of 75 subjects in the three treatment groups. To determine the power for the STAI state subscale, based on the STAI normative data (Spielberger et al., 1983), we use a mean of 35.5 with a  $SD$  of 10.5. Using the same approach as above for HR, we will have 90% power to detect a difference of 10 between any two groups with a sample size of 25. All sample size and power calculations were performed using PASS 13 (Hintze, 2014).

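### The SAP names no Aim 1 contrast and uses time point 1 as both outcome and covariate, so a condition main effect understates the post-baseline effect by one sixth, and by more if some phases show no effect

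*SAP*

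**What the plan says.** The Protocol's Background sets two directed questions under Aim 1. For the first, "the first mechanism we will test is whether social interaction with an animal buffers anxiety in the presence of a social stressor". The second is whether touch adds anything beyond social support. These correspond to social versus control, and social + physical versus social.

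Participants and Procedure lists six phases of the stress task: baseline, anticipation, preparation, speech, mental math and recovery. Baseline is a rest period. At the end "there will be a 30-minute recovery period where they will continue to watch the science documentary". The dog and handler are present in every phase in the two dog conditions.

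The SAP's Sample Size Calculation takes heart rate (HR) as the primary outcome and claims "90% power to detect a difference of 12 bpm between any two treatment groups", that is, pairwise differences.

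The SAP's Analyses section describes a three-way ANOVA with condition, continuous social anxiety and "one within-subjects factor, time point (1, 2, 3, 4, 5, 6". It then adds the time point 1 value of the outcome as a centered covariate. It does not say which term, contrast or phase answers the confirmatory hypotheses.

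**The concern.** There are three linked problems.

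- Time point 1 is on both sides of the model. It is one of the six outcome levels and also the covariate, so it can carry no adjusted condition difference, yet it counts as one sixth of any condition average.
- A condition main effect in this model weights all six phases equally. Baseline and recovery contain no stressor task. If the dog's effect is confined to the stressor, the reported effect is smaller than the effect the hypothesis is about.
- The Aim 1 questions and the power statement are pairwise, but no pairwise test is named. The analyst could choose afterwards among the main effect, the condition x time interaction and individual phases.

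At stake are the size of the reported effect, some power when effects are small or brief, and the confirmatory status of the Aim 1 result.

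**Working it through.** **1. The plan's own figure.** Inputs from the SAP's Sample Size Calculation: difference 12 bpm, SD 12 bpm ("of 12 bpm for baseline in all groups"), "a 0.05 significance level (alpha", and 90% power with 23 per group, "which we round to 25 per group for a total of 75 subjects in the three treatment groups". Two-sided testing is assumed because the SAP does not state it. The normal approximation gives n = 2(1.960 + 1.282)² x (12/12)² = 21.0, so 22. The two-sample t-test gives 22.02, so 23, with power 0.912 at 23 and 0.934 at 25. The figure reproduces. It applies to one heart-rate value per participant, not to an average over phases.

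**2. Keeping time 1 as an outcome level.** Let M be a participant's mean over phases 2-6. The six-phase mean is (Y1 + 5M)/6. Adjusting for Y1 removes the Y1 part completely and leaves 5/6 of the adjusted M. The condition estimate and its standard error both shrink by 5/6, so F and p do not change. In 200 simulated trials the largest difference between the two F statistics was about 1.3 x 10⁻¹³, and the ratio of estimates was 0.8333. A constant 12 bpm effect over phases 2-6 is reported as 12 x 5/6 = 10 bpm.

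**3. Phases without an effect.** Average effect in bpm, taking the effect as zero in all other phases:

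| True effect | Six-phase mean | Phases 2-6 | Phases 2-5 |
|---|---|---|---|
| 12 in phases 2-6 | 60/6 = 10.0 | 60/5 = 12.0 | 48/4 = 12.0 |
| 12 in phases 2-5 | 48/6 = 8.0 | 48/5 = 9.6 | 48/4 = 12.0 |
| 12 in speech and math only | 24/6 = 4.0 | 24/5 = 4.8 | 24/4 = 6.0 |
| 6 in phases 2-5 | 24/6 = 4.0 | 24/5 = 4.8 | 24/4 = 6.0 |

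The last two rows are the same, so they share the same power.

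**4. Power with the baseline covariate.** The documents give no correlation between phases. Assume SD 12 in every phase, correlation ρ from 0.5 to 0.8 (compound symmetry or AR(1)), 25 per arm, a pairwise contrast on 70 df and no dropout. The residual variance of a phase mean is its variance minus its squared covariance with time 1 divided by the variance of time 1. Under compound symmetry, for k phases, this is 12²[(1 + (k - 1)ρ)/k - ρ²]. The standard error is the residual SD x √(2/25).

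Example with compound symmetry and ρ = 0.5:
- Phases 2-6: variance 144(0.60 - 0.25) = 50.4, SD 7.10, SE 2.01. For 4.8 bpm, 4.8/2.01 = 2.39, power 66%.
- Phases 2-5: variance 144(0.625 - 0.25) = 54.0, SD 7.35, SE 2.08. For 6.0 bpm, 6.0/2.08 = 2.89, power 81%.

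Over all the assumed correlations:

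| True effect | Phases 2-6 (same test as six-phase) | Phases 2-5 |
|---|---|---|
| 12 in phases 2-5 | 98% to >99.9% | 99.9% or more |
| 6 in phases 2-5, or 12 in speech and math only | 53-88% | 71-97% |

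The ratio of standard errors, phases 2-5 to phases 2-6, runs from 0.99 to 1.06.

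**5. Which comparison is tested.** The omnibus condition F has 3 - 1 = 2 numerator df. Condition x time has (3 - 1)(6 - 1) = 10. Either can be significant without showing whether social differs from control or whether touch adds to social contact.

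**The case against.** The best defence is that the SAP never makes the condition main effect the Aim 1 test. A three-way ANOVA ordinarily includes condition x time, which can detect an effect confined to the stressor phases. That is correct, and a reader who infers that the plan commits itself to a diluted test goes further than the text. The documented fault is that no term is named. The interaction does not repair this: it tests any difference in profile and isolates neither the stressor phases nor the two mechanism comparisons.

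A reader might also infer that including baseline costs power. It does not, because time 1 is the covariate as well: only the estimate shrinks.

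Nor does the hypothesis by itself settle that recovery should be left out. The dog is present in all phases, recovery is one of the task's six phases, and no document says the effect stops there. The 30-minute length adds no weight either, since each time point counts once.

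Finally, the proposed window can dilute too. If only speech and math respond, phases 2-5 average 12 bpm down to 6 bpm. The choice of 2-5 is partly a judgement.

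**Conclusion.** The point holds as a fault of specification and estimation. Certain from the text: time 1 is both an outcome level and the covariate, no Aim 1 contrast is named, and a condition main effect would report 5/6 of the mean post-baseline effect (10 bpm for 12). Conditional on where the effect lies: 12 bpm is reported as 8.0 bpm if recovery shows none, and as 4.0 bpm if only speech and math respond.

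It would be tempting to conclude that the planned 90% power is lost. For 12 bpm across phases 2-5 it is not: the baseline-adjusted test keeps at least 98%. The loss is material for smaller or narrower effects, at about 53-88% against 71-97%. Such effects cannot be dismissed, since the SAP says it had no earlier data on the relative effects of the conditions.

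The power figures rest on the assumed correlations, equal SDs in all phases, effects that are equal in the affected phases and absent elsewhere, and no dropout. The 5/6 factor needs none of these. The plan should be changed, but the trial's size is not put in question by this point.

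**What to change.** In the SAP's Analyses section:

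1. Take time point 1 out of the outcome levels and use it only as the covariate.
2. Name the Aim 1 tests as two model-based heart-rate contrasts, social versus control and social + physical versus social, each on the mean of pre-specified stressor phases. Phases 2-5 (anticipation to mental math) are proposed. If the investigators prefer a narrower window, they should state it and give the reason.
3. Report recovery (phase 6) as a separate secondary contrast, so that a lasting effect is still seen.

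The cost is SAP wording only: no new data and no change in sample size. If the effect persists fully into recovery, the interval is up to about 6% wider than when averaging phases 2-6. The Analyses section is written in the past tense; if outcome data have already been examined, the contrasts should be labelled as specified afterwards.
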